7. DERIVED DATA

7.1. Baseline

For assessments that were collected on the daily monitoring chart, baseline is considered to be the subjects Day 1 assessment as collected on the CRF. For all other assessments, baseline is considered to be the subject's Day 0 assessment as collected on the CRF. If there are multiple assessments on Day 0 (or Day 1 for assessments from the daily monitoring chart) then the earliest will be taken as the baseline.

Change from baseline for post-baseline records will be calculated by subtracting the baseline value from the post-baseline value. If either the baseline or post-randomisation value is missing, the change from baseline is set to missing.

Percentage Change from Baseline will be calculated as

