7.2. Study Day

As noted in section 8.1, study days have been recorded or labelled differently across different CRF forms. Study days are recorded from day 1 to day 11 on the daily monitoring chart, day 1 to day 10 on the Emollient record and Calorie intake CRF and from day 0 to day 10 in the other CRFs. Therefore, it is possible that the same date will be assigned a different study days across different domains. Following review of interim analysis results, in order to resolve this inconsistency or confusion in reporting, all study visits will be presented from Day 0 to Day 10. See Table 2 below for further clarification.

Table 2: Clarification of Study day to be used during final reporting	

Label to be used throughout the final study report	Day as recorded in the Daily Monitoring Chart (CRF/Dataset)	Day as recorded in the Emollient record and Calorie intake (CREs/Datasets
Day 0	Day 1	Day 1
Day 1	Day 2	Day 2
Day 2	Day 3	Day 3
Day 3	Day 4	Day 4
Day 4	Day 5	Day 5
Day 5	Day 6	Day 6

Day 6	Day 7	Day 7
Day 7	Day 8	Day 8
Day 8	Day 9	Day 9
Day 9	Day 10	Day 10
Day 10	Day 11	

Note: Label Day 0 is also referred to as baseline in this RAP.

Assessments that were collected three times a day on the daily monitoring chart will have the time of assessment included in the day description. For example, day 1 will have the following labels: Day 1 9AM, Day 1 5PM and Day 1 1AM. For variables with multiple assessments on a given study day, first available assessment value will be used for the analysis.

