9.1. Weight

Derivations

Weight is collected once every day (approximately at 9 am) and recorded on 'daily monitoring chart' for all participants. However, for intervention group only, weight is measured three times daily (approximately at 9 am, 5 pm and 11 pm) and recorded on 'Emollient application record' to measure the intervention material. The summaries and analysis of weight gain will be based on the daily 9AM measurements on 'Daily monitoring chart' only, however, all measurements will be considered in the derivation of baseline weight. Data from baseline up to and including day 10 (labelled as Day 1 to Day 11 on the daily monitoring chart CRF) will be included in the weight analysis as per the specification on the eCRF. At the time of interim and post interim, a footnote will be included to indicate this.

Weight measurements that were collected while a subject had detectable oedema will be excluded from the summaries and analysis. The earliest measurement in the daily monitoring chart where oedema status was recorded as 1 (no oedema) will be taken as the baseline weight. Following review of the interim analysis results, it was decided that all subjects with oedema would be excluded from the weight analysis only. Subjects with oedema would be summarised separately in the final clinical study report.

Weight will be summarised as a rate of weight gain (g/kg/day), as defined below:

Change from Baseline in Weight at Day X (g)	=	Weight at Day X (g) – Weight at Baseline (g)
Relative Change from Baseline	=	Change from Baseline in Weight at Day X (g)

in Weight at Day X (g/kg)

Weight at Baseline (kg)

Rate of Weight Gain at Day X (g/kg/day) Relative Change in Weight at Day X (g/kg)

Note: 'X' refers to the study day label (see Table 2, page 10) and not the day reported on the daily monitoring chart

Summary Statistics

The following endpoints will be summarised by day (day 0 - day 10), presenting the number of subjects, mean (with standard deviation) and median, minimum and maximum for each treatment group. The summaries for change from baseline, relative change from baseline and rate of weight gain will also present summary statistics for the last day the subject was in the study.

- Weight (kg)
- Weight (kg) by oedematous status
- Change from baseline in weight (g)
- Change from baseline in weight (g) by oedematous status
- Relative change from baseline in weight (g/kg)
- Relative change from baseline in weight (g/kg) by oedematous status

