- Rate of weight gain (g/kg/day)
- Rate of weight gain (g/kg/day) by oedematous status

Relative change from baseline will also be plotted over time. Day will be presented on the x-axis and the relative change from baseline will be presented on the y-axis. The mean at each day will be presented with an associated 95% confidence interval (CI). The plot will be repeated for the rate of weight gain.

Additionally, the WAZ, WLZ and LAZ scores will be presented over time using simple descriptive statistics tables and graphical plots. Further exploratory statistical analyses may be performed for one or more Z scores if the review of data warrants so.

Mixed model repeated measures analysis

Rate of weight gain (g/kg/day) will be analysed using a mixed model repeated measures (MMRM) analysis with restricted maximum likelihood estimation and an unstructured variance-covariance matrix. Covariates/ factors will be included in the model as

described in Section 7.1**Error! Reference source not found.** In the circumstance that there are convergence problems with the MMRM analysis, this will be explored. For example the SCORING=4 option could be used in the MIXED statement, which makes SAS use Fisher scoring for the first 4 iterations. If the convergence problem cannot be resolved then alternative covariance structures will be investigated.

The estimate of treatment differences for "Emollient Therapy – No Emollient" at each day will be displayed in the summary of statistical analysis together with the 95% CI and the associated p-value. Least Squares Means for each day will also be presented with the standard error and the number of subjects contributing to the Least Squares Means.

The least squares mean at each day will be plotted by treatment group. Day will be presented on the x-axis and the rate of weight gain will be presented on the y-axis. The mean at each day will be presented with an associated 95% CI.

If any of the covariates are statistically significant then post-hoc analyses may be conducted to investigate further.

The normality assumptions will be assessed by inspection of the following plots:

Histogram of marginal studentised residuals derived from the MMRM model

• Normal probability plot

Bayesian analysis

At the interim analysis stage, Bayesian methods of analysis will be used to estimate the posterior distribution for the treatment difference in rate of weight gain between emollient therapy and no emollient at day 10 for the ITT population.

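### SAP 9.1 lets the baseline weight fall after Day 0 but ties X to the fixed study day label; if the rate divides by X, late-baseline children have their rate pulled toward zero (minor)

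*SAP*

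**What the plan says.** Section 9.1 (Weight, Derivations) sets a weight-specific baseline: "The earliest measurement in the daily monitoring chart where oedema status was recorded as 1 (no oedema) will be taken as the baseline weight". It adds: "Weight measurements that were collected while a subject had detectable oedema will be excluded from the summaries and analysis". A child with oedema on Day 0 therefore has a baseline on the later day when oedema is first recorded as absent.

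The rate is then defined from the relative change. What can be read of that line is "Rate of Weight Gain at Day X (g/kg/day) Relative Change in Weight at Day X (g/kg"), with no legible divisor. The note beneath says that X "refers to the study day label (see Table 2, page 10) and not the day reported on the daily monitoring chart". Table 2 in Section 7.2 runs those labels from Day 0 to Day 10 and states: "Note: Label Day 0 is also referred to as baseline in this RAP".

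Section 7.1 gives a different general rule: "For assessments that were collected on the daily monitoring chart, baseline is considered to be the subjects Day 1 assessment as collected on the CRF". That chart day is label Day 0. Section 7.1 also sets the change to missing when the baseline value is missing.

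After the interim, Section 9.1 excludes all children with oedema from the weight analysis and has them summarised separately in the final report. Note [1] to Table 1 counts 4 of them. The output list in 9.1 still includes "Rate of weight gain (g/kg/day) by oedematous status".

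**The concern.** The baseline moves with the child, but the day index does not. For a child whose baseline is Day 0, X equals the days elapsed and a rate per day can properly be formed by dividing by X. For a child whose baseline is Day b, the gain was accrued over X-b days. Dividing it by X spreads it over days on which no gain was counted.

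Section 9.2 shows that the authors handled this elsewhere: for time to discharge, the day is counted from the baseline. Section 9.1 has no such sentence, although its baseline is the one that can move and it derives the primary endpoint.

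At stake is mainly the description of children with oedema. Late baselines concentrate in that group, so it could appear to gain more slowly than the others partly because of the divisor.

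**Working it through.** The plan states no numerical rate, so there is no figure to reproduce. The check is algebra plus a count of who is reached.

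**Inputs.** Baseline day b: can exceed 0 under 9.1; the values below are assumptions. Day X: label 0 to 10 (Table 2). Divisor: inferred to be X, from the unit and the note. Constant true rate g in g/kg/day: assumption.

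**Formula.** Relative change at Day X = g(X-b). Divided by X, this is g(X-b)/X. Divided by elapsed days, it is g(X-b)/(X-b) = g. The factor applied to the true rate is therefore (X-b)/X.

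| Baseline day b | Factor at Day 5 | Factor at Day 10 | Day 10 rate if g = 5 |
|---|---|---|---|
| 0 | 1.00 | 1.00 | 5.0 |
| 1 | 4/5 = 0.80 | 9/10 = 0.90 | 4.5 |
| 2 | 3/5 = 0.60 | 8/10 = 0.80 | 4.0 |
| 3 | 2/5 = 0.40 | 7/10 = 0.70 | 3.5 |
| 4 | 1/5 = 0.20 | 6/10 = 0.60 | 3.0 |

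**Direction.** The pull is toward zero, not always downward. With g = -2 and b = 3, Day 10 gives -2 × 0.70 = -1.4, so a loss looks smaller.

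**Edge days.** At X = b > 0 the formula returns 0/b = 0, an artificial zero entering that day's summary. At X = 0 it is 0/0, although the summaries are listed from Day 0.

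**Who is reached.**
- *Descriptive oedema outputs.* Section 6.1 classes a child as oedematous if oedema is recorded at any time in the study. A child free of oedema on Day 0 who develops it later still has b = 0. Of the 4 known at interim, anywhere from 0 to 4 could have a late baseline.
- *Final MMRM.* Children with oedema contribute nothing. A late baseline can arise only for a child without oedema who lacks a Day 0 weight or oedema entry. The number is not given.
- *Handling of those children.* With no Day 0 weight, 9.1 moves to a later baseline while 7.1 sets the change to missing. With a Day 0 weight but no oedema entry, 9.1 again moves on, while 7.1 would use the Day 0 weight. No sentence says which governs.

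**Scale at interim, for context only.** The interim followed an earlier version of the analysis plan that is not at hand. If the same rule applied, with all 4 children in one arm of about 50 (assumed even split of about 100), g = 5 and b = 3, the arm mean shifts by 4/50 × 5 × 0.3 = 0.12 g/kg/day. Over g = 2 to 10 and b = 1 to 5 the range is 0.016 to 0.40. A 2:2 split with equal b and g leaves the treatment difference unchanged.

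**The case against.** The strongest reply is that the premise cannot be read in the document. The divisor is missing from the text at hand, and a symbol lost in reading a file is not an error in the plan. The note on X does not settle the matter alone, because X also indexes the weights in the numerators and would need defining whatever the divisor is. This stands as a condition on the point. Division by X remains the likelier reading: a rate per day needs a day count, X is the only one defined, and the longer denominator of the neighbouring formula (baseline weight in kg) is legible, which fits a short symbol having dropped out. If the formula divides by days since the child's own baseline, the distortion disappears.

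A reader might infer that the primary comparison is biased. The documents do not support that. The only late baseline the plan itself creates comes from oedema, and those children are excluded from the final weight analysis. The remaining route needs missing Day 0 entries, and nothing in the SAP shows that any exist.

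A reader might also infer that every late-baseline child has an understated rate. That is too broad: a weight loss is understated in size, so the signed rate is too high, and no change stays at zero.

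Finally, the SAP contains no miscalculated figure. This is a derivation rule left loose, and it should be reported as that.

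**Conclusion.** The mismatch is real and minor. Section 9.1 combines a baseline that can move with a day label that cannot. Conditional on the divisor being X, a late-baseline child's rate is multiplied by (X-b)/X, a shrinkage of 10% at Day 10 for an assumed b = 1 and 40% for b = 4, and larger on earlier days. This bears on the rate tables by oedematous status and on the separate oedema summary, for those children who had oedema on Day 0. The final MMRM is unaffected by children with oedema. Any effect there depends on an unstated number of children without oedema who have an incomplete Day 0 record, and for them the conflict between 7.1 and 9.1 needs settling in any case.

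**What to change.** In Section 9.1, define the rate at Day X as the relative change at Day X divided by (X minus the study day of the child's baseline weight), only for X after that day. Use the definition in all summaries and in the MMRM. If the formula already divides by days since the child's own baseline, say so in words.

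Add one sentence stating whether 7.1 or 9.1 governs when the Day 0 weight is missing, and likewise when only the Day 0 oedema entry is missing. Report how many children without oedema this concerns.

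The cost is one line of derivation and one sentence. Results for children with a Day 0 baseline do not change.

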9.2. Time (days) to discharge from acute phase

Derivations

Discharge from the acute phase is based on improvement in mental state, normalisation of vital signs, re-establishment of oral feeding and resolution of all acute illnesses.

The CRF collects information on whether a patient is ready for discharge from the acute phase (Y/N) daily. Time (days) will be derived as the number of days between baseline and the first occurrence where 'Ready for discharge from acute phase' was recorded as Yes. Baseline will be taken as the earliest measurement recorded in the daily monitoring chart. Day will be derived relative to the baseline.

If a subject withdrew or died before being ready for discharge from the acute phase then they will be censored at the time they left the study. Patients who completed Day 10 before being ready for discharge will be followed up by the site until they withdraw or are ready for discharge.

Kaplan Meier

A Kaplan-Meier plot including 95% CIs and the number of subjects at risk at each day will be presented.

Cox Proportional Hazards

The time to discharge from acute phase will be compared between treatment groups using a Cox's Proportional Hazards model adjusting for the covariates specified in Section 7.1.

The time to discharge from acute phase will be presented in quartiles for each group. The hazard ratio, 95% CI and associated p-value will also be presented.

Residual plots from the Cox proportional hazard model and the Kaplan-Meier plot will be used to visually check the assumption of proportional hazards is fair. If the proportional hazard assumption is invalid, then other methods of analysis may be considered which do not make this assumption, for example a Weibull model may be fitted to the data.

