6.1. Strata and Covariates

Randomisation was planned to be stratified by age at baseline in two strata: 2-<6 months and 6-24 months in a 1:2 ratio. However, as noted in the amended protocol, additional subjects may be enrolled in the older subgroup.

The two age group strata (2-<6 months and 6-24 months) will be the categories used in all tables, figures and listings split by age group unless stated otherwise.

The statistical analysis will be adjusted for age at baseline (as a continuous covariate), sex and a measure of the parameter or severity at baseline as specified in the table below. In addition, the analysis of weight gain will include average calorie intake divided by baseline weight (calorie intake per day per kg).

Patients will be categorised as "Oedematous" if they are recorded on the CRF as having oedema at any time during the study. Otherwise they will be categorised as "Non-oedematous". For each patient, the daily calorie intake (total energy per day) is collected on the CRF. The average of these values divided by baseline weight will be used as the calorie intake covariate.

If an inadequate number of subjects is observed in one of the categories for sex or oedematous status then the covariates may be removed from the models.

In addition to the above, differences between the two treatment groups (emollient therapy versus no emollient) will be examined with respect to baseline characteristics prior to performing statistical analysis of the efficacy endpoints. If any differences are considered to be clinically important, exploratory subgroup analysis may be presented for the relevant endpoints.

Depending on the method of statistical analysis, covariates/factors specified below will be fitted in each model. If any terms are not significant then they may be dropped from the final analysis.

Method of analysis	Endpoints]	Fixed effects te	erms	Random effects terms
		Continuous Covariates	Factors	Interactions	Covariates
ANCOVA	Fatty Acids	Baseline of parameter, age	Treatment, sex		
MMRM	Weight	Baseline of parameter,	Treatment, day, sex,	Baseline of parameter	Subject (in the subject
	TEWL	age, calorie intake per	oedematous status	*day, treatment*day,	option of the repeated
	Skin redness	day per kg ^[2] , mean breast		treatment*age category, treatment*age	statement in proc mixed)
	Skin Appearance	feeding frequency ^[2]		category*day ^[3]	
Cox	Discharge	Baseline	Treatment,		
proportional	from acute	weight-for-	sex		
hazard	phase	length Z			

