8.3. Baseline Characteristics

Summary statistics for the weight-for-length Z (WLZ) score, length-for-age Z (LAZ) score, weight-for-age Z (WAZ) score, mid upper arm circumference, mother's / caregiver's formal years of education, father's formal years of education and duration of exclusive breast feeding at Day 0 will be summarised by treatment group for the Safety population. The number and percentage of subjects will also be presented for, presence of oedema, breast feeding history (no breast feeding since birth, partial breast feeding or exclusive breast feeding), breast feeding status (still breast feeding, not still breast feeding), type of diarrhoea and presence of pneumonia, sepsis/septicaemia, meningitis/encephalitis, vitamin A deficiency, skin infection, ileus, ASOM/CSOM, enteric fever and other clinical diagnosis and visible wasting at Day 0.

For the interim analysis only, differences between the two treatment groups (emollient therapy versus no emollient) for each baseline characteristic will be examined. For continuous data a two sample t-test will be carried out to compare the two treatment groups. If the data is not normally distributed then a non-parametric Wilcoxon rank sum test may be used instead. For categorical data a chi-squared test will be used.

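### The Cox model for time to discharge omits the Day 0 acute illnesses whose resolution is part of the event: the analysis stays valid, but loses efficiency and protection from chance imbalance

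*SAP*

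**What the plan says.** Time to discharge from the acute phase is the first-listed secondary endpoint (SAP 1.2). Section 9.2 states what the event depends on: "Discharge from the acute phase is based on improvement in mental state, normalisation of vital signs, re-establishment of oral feeding and resolution of all acute" (cut before the final word, illnesses). The arms are compared with a "Cox's Proportional Hazards model adjusting for the covariates specified in Section 7.1". The covariates are in fact in Table 1 of section 6.1; section 7.1 is headed Baseline.

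Section 6.1 states the general rule that analyses are "adjusted for age at baseline (as a continuous covariate), sex and a measure of the parameter or severity at baseline". For discharge, Table 1 fills this in with baseline WLZ, next to age, sex and treatment.

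Section 8.3 lists what is known about acute illness at Day 0: "type of diarrhoea and presence of pneumonia, sepsis/septicaemia, meningitis/encephalitis, vitamin A deficiency, skin infection, ileus, ASOM/CSOM, enteric fever and other clinical diagnosis". These items are summarised by arm. No section brings them into the Cox model.

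Randomisation was planned to be stratified by age only (6.1). On baseline differences, section 6.1 says: "If any differences are considered to be clinically important, exploratory subgroup analysis may be presented for the relevant endpoints". It also says: "If any terms are not significant then they may be dropped from the final analysis".

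**The concern.** A child admitted with pneumonia or sepsis has a condition to clear before the event can occur, and a child without it does not. Day 0 illness can therefore be expected to predict time to discharge from the event definition alone. WLZ measures wasting, which is not one of the four discharge criteria.

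Leaving a prognostic factor out of a Cox model has two consequences. The HR is averaged over that factor, so it lies nearer to 1 than the HR conditional on it, and the test has less power. In addition, any chance difference between arms in admission illness stays in the reported HR. A subgroup analysis could describe such a difference, but it is optional and would leave the overall estimate unchanged.

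**Working it through.** **No planned figure to reproduce.** The SAP gives no event count, target HR or power for this endpoint and refers sample size to the protocol. The size of the effect was therefore simulated.

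**Inputs from the SAP:** the covariate list (Table 1), time counted in days and censoring at withdrawal or death (9.2), and about 100 evaluable children at the interim (section 3).

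**Assumed inputs:** final N of 200 as an alternative to 100; control discharge hazard 0.25 per day; about 5% censoring; one yes/no Day 0 illness in 30%, 40% or 50% of children, multiplying the discharge hazard by 0.7, 0.5 or 0.33; conditional treatment HR of 1.5 or 1.0; equal arms.

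**Method:** exponential times rounded up to whole days, Efron ties, two-sided 5% Wald test, 600 replicates at N=100 and 400 at N=200 for HR 1.5. The Monte Carlo error of each power is about 2 points. WLZ, age and sex were not simulated.

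**Check on the set-up** (Schoenfeld): power = Φ(|ln HR| × √(events/4) − 1.96).
- 95 events, HR 1.5: Φ(0.405 × 4.87 − 1.96) = Φ(0.02) = 51%.
- 190 events, HR 1.5: Φ(0.405 × 6.89 − 1.96) = Φ(0.83) = 80%.

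The adjusted powers below (45–51% and 76–82%) agree with these.

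**Results, conditional HR 1.5, illness omitted → adjusted:**

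| N, prevalence | Illness hazard multiplier | Estimated HR | Power (%) | Gain (points) |
|---|---|---|---|---|
| 100, 30% | 0.7 | 1.50 → 1.52 | 50.0 → 50.2 | 0.2 |
| 100, 50% | 0.7 | 1.49 → 1.50 | 47.0 → 48.8 | 1.8 |
| 200, 40% | 0.7 | 1.49 → 1.51 | 81.0 → 81.8 | 0.8 |
| 100, 30% | 0.5 | 1.47 → 1.53 | 44.0 → 50.5 | 6.5 |
| 100, 50% | 0.5 | 1.46 → 1.52 | 44.8 → 50.0 | 5.2 |
| 200, 40% | 0.5 | 1.46 → 1.51 | 71.3 → 76.0 | 4.7 |
| 100, 30% | 0.33 | 1.38 → 1.48 | 33.3 → 44.8 | 11.5 |
| 100, 50% | 0.33 | 1.41 → 1.51 | 34.2 → 46.7 | 12.5 |
| 200, 40% | 0.33 | 1.41 → 1.52 | 60.8 → 76.5 | 15.7 |

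**Level of the test.** With HR 1.0 and no built-in imbalance, rejection rates over ten scenarios were 3.0–6.3% with illness omitted and 4.2–5.8% with it included. The Monte Carlo error is about √(0.05 × 0.95/600) = 0.9 points, so both scatter around 5%.

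**Chance imbalance.** The SD of the difference in prevalence between arms at 40% is √(0.4 × 0.6 × 4/N): 6.9 points at N=200 and 9.8 at N=100. A 10-point difference is thus 1.44 SD at N=200 and 1.02 SD at N=100. By the normal approximation, a difference at least that large in either direction arises in about 15% and 31% of trials. With 10 points more illness in the treated arm, N=200 and no treatment effect, the HR with illness omitted averages 0.97, 0.92 and 0.91 for multipliers 0.7, 0.5 and 0.33. With illness included it averages 1.01, 0.98 and 1.00.

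**A more favourable scenario.** Two independent illnesses, each in 50% of children (Weibull times with shape 1.5, 1,000 replicates):
- N=200, HR 1.5: gains of 4.3, 12.1 and 21.8 points at multipliers 0.7, 0.5 and 0.35.
- N=100, HR 1.75: gains of 3.1, 15.9 and 22.5 points.
- Illness with no effect on discharge: the extra terms cost 0.2 and 0.8 points.

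**The case against.** **The plan breaks no rule of its own.** A reader might infer that the Cox row contradicts section 6.1. It does not: the rule allows a measure of the parameter or of severity, time to discharge has no baseline value, and WLZ is a severity measure. The logistic row for nosocomial infection does the same. This stands, and the point is only that the SAP holds a more direct measure than the one it uses.

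**The HR is not biased.** A reader might take the shift toward 1 as bias or as an invalid test. It is non-collapsibility: the HR averaged over illness is a different, valid quantity from the HR conditional on it, and the test keeps its level. Chance imbalance is also part of the sampling variation that the confidence interval covers. At about 190 events SE(ln HR) is √(4/190) = 0.145, so the shifts above are |ln 0.971|/0.145 = 0.2 to |ln 0.908|/0.145 = 0.67 standard errors. This stands.

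**Prognostic strength is inferred.** Illness resolution is one of four criteria, and a yes/no diagnosis at admission does not measure time to resolution. A near-universal or rare diagnosis would gain little, and correlation with WLZ or age would shrink the gain. This limits the size but does not remove the case, because the link follows from the event definition.

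**The choice can no longer be fully blind to arm.** Section 8.3 planned tests of each baseline characteristic by arm at the interim, and interim results have been reviewed. This is a real cost. It is contained by choosing on clinical grounds and showing the planned model alongside.

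**Conclusion.** The omission is confirmed in Table 1, and no other section of the SAP fills it. The loss is of efficiency and of protection from chance imbalance in admission illness. It is not a loss of validity.

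The gain from adjustment is negligible if illness is weakly prognostic and becomes worth having once illness roughly halves the discharge hazard. A reader might expect a 5-point gain already at a multiplier of 0.7. Even two common illnesses give only 3–4 points there, so that threshold lies between 0.7 and 0.5. Gains of 12 to 22 points at multipliers of 0.5 and 0.35 need the favourable two-illness scenario and should not be taken as typical.

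All of this rests on assumed prevalence, prognostic strength and sample size. The endpoint is secondary, every analysis is declared exploratory (section 6), and no power target is stated for it in the SAP. The change is worth making because an HR, confidence interval and p-value will be reported and the data are already collected.

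**What to change.** In the Cox row of Table 1, add a short fixed set of Day 0 factors: pneumonia (yes/no), sepsis/septicaemia (yes/no) and type of diarrhoea. If counts pooled over arms are sparse, use one count of acute diagnoses instead. Keep WLZ, age and sex.

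- Choose the set on clinical relevance and on frequency pooled across arms, not on observed differences between arms.
- Exempt these terms from the rule in section 6.1 that lets non-significant terms be dropped.
- Report the currently specified model alongside, and label the addition as made after the interim. Section 1.2 allows the plan to be updated at that stage.
- Correct the reference in section 9.2 so that it points to section 6.1.

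The cost is one line in Table 1, one more model run and a few extra parameters (under 1 point of power in the two-illness simulations if illness turns out not to matter). The remaining drawback is a covariate choice made after interim results were seen, which is why both models should be shown.

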6. GENERAL CONSIDERATIONS FOR DATA ANALYSES

All programming will be performed using - SAS (version 9.4 or later), SPSS or STATA. The analysis will be carried out in collaboration with icddr,b, and Stanford University. Further analysis of the SCORDoK score may be carried out by the Denmark SCORDoK team. The metabolomic data will be analyzed by the CRO assaying the samples (Metabolon) with input from representatives from the R&D Platform Technology & Science group within the GSK subsidiary company Cellzome All analyses will be deemed exploratory.

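### Time to discharge is counted in whole days, so event times will be tied, but the Cox model in SAP 9.2 names no tie method; the Breslow approximation would pull the hazard ratio toward 1

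*SAP*

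**What the plan says.** Section 9.2 of the SAP sets the time scale in two steps. The record is daily: "The CRF collects information on whether a patient is ready for discharge from the acute phase (Y/N) daily". The duration is a day count that ends at the first positive entry: "Time (days) will be derived as the number of days between baseline and the first occurrence where 'Ready for discharge from acute phase' was recorded". Children who leave or die first are censored on departure ("If a subject withdrew or died before being ready for discharge from the acute phase then they will be censored at the time they left"), and those not ready by Day 10 stay under observation: "Patients who completed Day 10 before being ready for discharge will be followed up by the site until they withdraw or are ready for discharge".

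The analysis follows: "The time to discharge from acute phase will be compared between treatment groups using a Cox's Proportional Hazards model". Table 1 in section 6.1 lists the terms: treatment, sex, baseline weight-for-length Z score and age. On output, section 9.2 says: "The hazard ratio, 95% CI and associated p-value will also be presented".

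No tie method appears in 9.2, in Table 1 or elsewhere. The only fallback in 9.2 is for non-proportional hazards. Section 6 leaves the software open, without assigning a package to this model: "All programming will be performed using - SAS (version 9.4 or later), SPSS or STATA".

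**The concern.** The Cox partial likelihood is exact only when event times are distinct. With ties, the analyst must choose an approximation (Breslow, Efron), an exact form or a discrete-time model. These agree when ties are rare and diverge when a large share of the children still at risk have the event on the same recorded day. A once-daily record in a study of about 100 or more children makes ties certain.

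Two things follow. The reported hazard ratio, CI and p-value are not fully determined by the plan. And one routine choice, Breslow, is biased toward no effect on such data, whichever arm does better. An exploratory study that makes no multiplicity adjustment (section 6.2) leans on its effect estimates, so attenuation caused only by the recording grid is worth avoiding.

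**Working it through.** The SAP states no hazard ratio, event count or power for this endpoint, so there is no figure to reproduce.

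**Inputs from the SAP:** a daily yes/no record, whole-day times, a Cox hazard ratio, censoring at withdrawal or death (9.2), and about 100 evaluable children at interim (section 3).

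**Assumptions, not in the SAP:** control median 3 to 10 days; 50 or 100 children per arm, 1:1; Weibull proportional hazards with shape 1 (flat hazard) or 2 (discharges more clustered), rounded up to whole days; about 10% of children given a censoring time; treatment as the only covariate.

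**Step 1: what Breslow estimates.** On one day let n1 and n0 children be at risk and d1 and d0 be discharged. The Breslow score equation is d1 − (d1 + d0)·n1θ/(n1θ + n0) = 0, which solves to θ = (d1/n1)/(d0/n0). That is the ratio of daily discharge probabilities, not the ratio of hazards. With a flat hazard and control median m, these probabilities are the same every day:

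- control: p0 = 1 − 2^(−1/m)
- emollient: p1 = 1 − 2^(−HR/m)

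so in large samples Breslow tends to p1/p0.

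| m (days) | p0 | p1 (HR 1.5) | Breslow limit p1/p0 |
|---|---|---|---|
| 3 | 0.2063 | 0.2929 | 1.42 |
| 5 | 0.1294 | 0.1877 | 1.45 |
| 7 | 0.0943 | 0.1380 | 1.46 |
| 10 | 0.0670 | 0.0987 | 1.47 |

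The complementary log-log scale recovers the hazard ratio. For m = 3, −ln(1 − 0.2929) = 0.3466 and −ln(1 − 0.2063) = 0.2310, and 0.3466/0.2310 = 1.50. At HR 1, p1 = p0, so Breslow is centred on 1 under the null.

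**Step 2: finite samples.** Breslow and Efron were fitted to the same simulated daily data, 400 trials per setting, true HR 1.5:

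| Children in total | Median (days) | Shape | Breslow HR | Efron HR | Power, Breslow v Efron |
|---|---|---|---|---|---|
| 200 | 3 | 1 | 1.43 | 1.51 | 73% v 81% |
| 200 | 3 | 2 | 1.38 | 1.50 | 62% v 82% |
| 200 | 7 | 1 | 1.48 | 1.52 | 76% v 81% |
| 100 | 5 | 2 | 1.45 | 1.52 | 40% v 52% |
| 100 | 7 | 1 | 1.46 | 1.50 | 42% v 45% |
| 200 | 10 | 1 | 1.50 | 1.52 | 74% v 77% |

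Over medians of 3 to 7 days, both shapes and both sizes, Breslow averages 1.36 to 1.48 and Efron 1.47 to 1.52. At a median of 10 days Breslow reaches 1.47 to 1.50 across runs. On the log scale Breslow is 0.79 to 0.95 of Efron over true HRs of 1.3, 1.5 and 2.0, an attenuation of 5 to 21%.

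**Step 3: power.** With 2,000 trials per setting over the same medians (3, 5, 7 days), shapes and sizes, Breslow's power at HR 1.5 is lower in all 12 settings, by about 4 to 19 points. The 400-trial runs reach 82.3 − 61.8 = 20.5 points in the most tied setting, which Monte Carlo error does not separate from 19. The smallest loss is 3 points (median 10 days).

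**Step 4: type I error.** At HR 1 with 2,000 trials, rejection is 1.4 to 4.2% with Breslow and 4.2 to 5.9% with Efron. Efron's higher power does not come from an inflated test.

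**Step 5: scale against noise.** With 100 per arm and median 3 days the shift is ln(1.505/1.429) = 0.052, or 0.052/0.148 = 0.35 of a standard error (shape 1), and ln(1.499/1.379) = 0.083, or 0.083/0.147 = 0.57 (shape 2).

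**The case against.** The strongest reply is that the SAP does not choose Breslow. It leaves the option open, and a programmer could set Efron without departing from the text. This stands: the bias is conditional on a choice the document does not make, and the default behaviour of the packages is not in the SAP. It does not remove the point. The plan still leaves the estimate undetermined, and it fixes options of this kind elsewhere (SCORING=4, the Jeffreys prior and the OM option, all in 9.1).

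The size also rests on assumptions. Nothing in the SAP says that most discharges fall within ten days, and 9.2 provides for follow-up beyond Day 10. With small effects little is lost: at a true HR of 1.2, a median of 6 days and 100 per arm, Breslow gives 1.18 and Efron 1.20, with power of 20% and 22%. The direction is the same in every non-null setting.

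The consequence is limited. Time to discharge is one of several unranked secondary endpoints, all analyses are deemed exploratory (section 6), the SAP sets no power target for this endpoint, and the Kaplan-Meier curve and quartiles do not use the tie method.

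A reader might infer that the reported hazard ratio will be understated as a matter of fact, or that the test produces false positives. The document supports neither: the first depends on the method actually run, and under Breslow the test is conservative.

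**Conclusion.** The point holds as a specification gap with a known direction of harm. Whole-day recording guarantees ties, and the plan names no way to handle them. If Breslow is used, the hazard ratio moves toward 1 by about 5 to 21% on the log scale for medians of 3 to 7 days, and by less at 10 days. For a true ratio of 1.5 that is about 1.36 to 1.50 instead of about 1.47 to 1.52, at a cost of roughly 3 to 20 points of power. These figures rest on the assumed medians, curve shapes, arm sizes and light censoring. The shift stays within about 0.6 of a standard error at 100 per arm with a true ratio of 1.5, so it would seldom reverse a conclusion alone. This is a worthwhile correction to a secondary, exploratory analysis and does not put the study's main result in doubt.

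**What to change.** In section 9.2, state that the Cox model uses Efron (or exact) handling of tied event times, with the covariates already listed in Table 1, and name a package for this analysis that supports it. An acceptable alternative is a discrete-time model with a complementary log-log link and day as a factor, with the same covariates; it estimates the same hazard ratio directly from daily data. The cost is one sentence in the SAP and one code option. No new data are needed, and the runs show no material type I error cost.
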